11.3.2 Hypothesis, analysis methods and performance requirements

The null hypothesis that will be tested is that the hazard ratio for aCRT versus control is equal to 1. It will be tested against the alternative hypothesis that the hazard ratio is unequal to 1.

Let $S_T(t)$ and $S_C(t)$ denote the proportion of patients in the treatment arm and control arm, respectively, that have not experienced a primary endpoint up to time t . Let $h_T(t)$ and $h_C(t)$ be the associated hazard functions. Under the proportional hazards model, $h_T(t) = HR h_C(t)$, where HR is the hazard ratio of treatment compared to control. The null and alternative hypotheses can be expressed as:

$$H_0 : HR = 1$$

$$H_A : HR \neq 1$$

The hypothesis will be tested using a Cox proportional hazards regression model with a random center effect (frailty), stratified by baseline NYHA class. The hazard ratio for treatment arm versus control arm will be reported with its associated p-value and 95% confidence interval. The null hypothesis will be rejected when the p-value is below the critical value for the (interim or final) analysis, and it will be concluded that aCRT reduces the incidence of the primary endpoint when the hazard ratio is below 1. Kaplan-Meier graphs for incidence will also be reported, together with an estimate for the absolute event rate difference at 2 years post randomization.

Two further analyses of the primary objective are planned. First, a Cox regression model will be reported with a random center effect and a risk score as fixed effect. The risk score will be derived from baseline data. Second, an analysis will be done including only the patients for whom the ECG Core Laboratory confirmed the presence of LBBB.

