11.5.1 Secondary objectives

To assess all-cause mortality in the aCRT ON arm compared to aCRT OFF.

Mortality will be illustrated with Kaplan-Meier graphs. A Cox proportional hazards regression model will be used to estimate the HR of aCRT compared to control, which will be reported with its p-value and 95% confidence interval. The model will include the stratification variables also included in the primary objective model.

To assess the rate of intervention for heart failure decompensation for aCRT ON compared to aCRT OFF.

Incidence of intervention for heart failure decompensation will be illustrated with cumulative incidence graphs. A Cox regression model will be used to estimate the cause-specific HR of aCRT compared to control, which will be reported with its p-value and 95% confidence interval. The model will include the stratification variables also included in the primary objective model. Additionally, recurrent event survival analysis will be performed to compare rates of interventions for heart failure decompensation.

To test the hypothesis that aCRT ON increases the proportion of patients that improve on the Clinical Composite Score (CCS) compared to aCRT OFF, at 6 months of follow-up.

The Clinical Composite Score classifies patients according their clinical status at 6 months post randomization into categories Improved, Unchanged, and Worsened²². A patient is classified Worsened in case of death, hospitalization for worsening heart failure, worsened NYHA class (using last observation carried forward), or worsened status on the Global Assessment Score. Also patients that exit the study or cross over because of worsening heart failure are classified Worsened. A patient is classified Improved when not Worsened and there is an improvement in NYHA class or Global Assessment Score. Patients that are not Worsened or Improved are Unchanged.

The proportion of patients who Improved will be compared between the arms of the study with a logistic regression model, correcting for the stratification variables also included in the primary objective model.

To test the hypothesis that aCRT reduces the incidence of AF compared to aCRT OFF.

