Incidence of AF will be determined from device data, and the endpoint for the primary analysis will be the first day after randomization on which there is >6 hrs of AF reported in the device's Cardiac Compass Trends. The analysis will compare incidence of AF using survival analysis methods. As secondary analyses device measured AF burden and treatment for AF will be analyzed.

To test the hypothesis that the change in quality of life, measured by the KCCQ, in the aCRT ON group is better than the change in the aCRT OFF group.

The parameter of interest is the KCCQ overall summary score (range, 0 to 100; higher scores indicate better health status) which will be assessed at baseline and at the 3, 6, 12, 18, and 24 months follow-up visits. The summary score at the follow-up visits will be analyzed using a linear mixed effects regression model that will account for the correlation of scores within each patient. The treatment arm allocation will be included as a main effect. The baseline KCCQ score as well as the stratification variables included in the primary objective model will be included as covariates in the model. Analysis will be corrected for time trends if needed.

To test the hypothesis that the change in health outcome, measured by the EQ-5D, in the aCRT ON group is better than the change in the aCRT OFF group.

The parameter of interest is the EQ-5D index, which will be assessed at baseline and at the 3, 6, 12, 18, and 24 months follow-up visits. Derivation of the index will follow instructions provided by the EuroQol Group (www.euroqol.org). The index at the follow-up visits will be analyzed using a linear mixed effects regression model that will account for the correlation of measurements within each patient. The treatment arm allocation will be included as a main effect. The baseline EQ-5D index as well as the stratification variables included in the primary objective model will be included as covariates in the model. Analysis will be corrected for time trends if needed.

To test the hypothesis that aCRT reduces the incidence of all-cause re-admissions after a heart failure (HF) admission within 30-days of the index event.

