3 RATIONALE FOR STUDY DESIGN

The study design and rationale can be found in the CIP. AdaptResponse is a prospective, randomized, controlled, interventional, single-blinded, multi-center, post-market, global Cardiac Resynchronization Therapy (CRT) in heart failure (HF) clinical study. The purpose of this clinical study is to test the hypothesis that market released CRT devices which contain the AdaptivCRT® (aCRT) algorithm have a superior outcome compared to standard CRT devices in CRT indicated patients with normal atrio-ventricular (AV) conduction and left bundle branch block (LBBB).

Following enrollment and baseline assessment, eligible subjects will be implanted with a CRT system containing the aCRT algorithm and randomized in a 1:1 fashion to either treatment (aCRT ON) or control (aCRT OFF) groups. **aCRT ON** means CRT therapy with ambulatory optimization and preferential LV-only pacing; **aCRT OFF** means standard bi-ventricular CRT therapy. The randomization will be stratified by two factors: site and NYHA class at enrollment. The primary objective is to compare the incidence of the combined endpoint of all-cause mortality and intervention for heart failure decompensation between the aCRT ON and aCRT OFF groups. Because the event rate is expected to be relatively low, the study utilizes an “event-driven” design that requires a review of accumulating endpoint events during the trial to possibly modify enrollment goal and follow-up duration in order to maintain study power. Study subjects will be followed until the required number of endpoint events is reached and/or a decision by Medtronic, Ethics Committee, or regulatory authority, whichever occurs first.

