4.4.5 Secondary Objective #5: Quality of life measured by KCCQ

The secondary objective #5 is to test the hypothesis that the change in quality of life, measured by the Kansas City Cardiomyopathy Questionnaire (KCCQ), in the aCRT ON group is better than the change in the aCRT OFF group

Hypothesis

The KCCQ questions are categorized into clinically relevant domains²⁰

- Physical limitation (question 1: 6 subquestions),
- Frequency of symptoms (questions 3, 5, 7 and 9),
- Severity of symptoms (questions 4, 6 and 8),
- Symptom stability (question 2),
- Self-efficacy and knowledge (questions 10 and 11),
- Social limitation (question 15: 4 subquestions) and
- Quality of life (questions 12, 13 and 14).

A score for each domain will be calculated. Also, total symptom score is the average of symptom frequency score and symptom severity score. In addition, two summary scores will be calculated:

- Clinical Summary Score: mean of physical limitation score and total symptom score;
- Overall Summary Score: mean of physical limitation score, total symptom score, quality of life score, and social limitation score.

Hypothesis testing will be performed on the overall summary score. Summary statistics will be provided for the other scores by study arm.

The KCCQ questionnaire is collected at baseline and at the 3, 6, 12, 18, and 24 months follow-up visits. The overall summary score (range, 0 to 100; higher scores indicate better health status) will be assessed. Let α_T and α_C denote the fixed treatment effect on KCCQ overall summary score for aCRT ON and aCRT OFF group, respectively. The null and alternative hypotheses are:

$$H_0 : \alpha_T = \alpha_C$$

$$H_A : \alpha_T \neq \alpha_C$$

Analysis Method

General linear mixed models will be used to analyze the continuous KCCQ overall summary score collected over time. In the primary analysis, the model will include the fixed effects of treatment, visit, treatment by visit interaction and baseline KCCQ score, and two random effects - random site effect and random subject effect:

$$Y_{ijk} = \mu + \alpha_i + \beta_j + \tau_{ij} + \lambda_{kg} + \gamma_k + \eta_{i(g)} + \varepsilon_{ijk}$$

Here:

- μ is the common intercept of the model
- α_i is the i th fixed treatment effect, $i=T, C$;
- β_j is the j th fixed visit effect, $j=1, 2, \dots, J$;
- τ_{ij} is the fixed interaction effect between i th treatment and j th visit;
- λ_{kg} is the fixed baseline KCCQ effect of g th subject in k th site;

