- γ_k is the random site effect for the k th site, $k= 1, 2, \dots, K$;
- $\eta_{i(g)}$ is the random subject effect of g th subject in i th treatment group, $g=1, 2, \dots, G$;
- ε_{ijk} is the random error for the g th subject from k th site having i th treatment at j th visit.

The analysis will be conducted using the SAS MIXED procedure similar to below:

```
proc mixed data=KCCQ method=reml covtest;
  id pt;
  class pt site rand visit;
  model KCCQscore = rand visit rand*visit KCCQ_base
                / solution ddfm=satterth covb chisq;
  random site pt(rand);
run;
```

where KCCQscore is a continuous longitudinal endpoint that includes all post-randomization KCCQ measurements, visit is the categorical version of the visit number, rand*visit is the interaction between treatment and visit, and KCCQ_base is the KCCQ score at baseline. If the interaction between treatment and visit is not significant, it will be eliminated from the model and the main effect of treatment will be used to test the hypotheses; otherwise, if the treatment by visit interaction turns out to be significant, then treatment effect at each visit will be evaluated and the hypotheses will be tested using CONTRAST or LEMESTIMATE statement in the SAS MIXED procedure.

Missing Data

Missing data for individual KCCQ questions will be handled as suggested by the questionnaire authors¹⁹. Missing values within each domain are assigned the average of the answered items within that same domain. Scale scores are transformed to a 0 to 100 range by subtracting the lowest possible scale score, dividing by the range of the scale and multiplying by 100.

To investigate whether patients with missing KCCQ data are missing at random (MAR), the baseline characteristics between patients with missing data on KCCQ and those with complete data will be compared. If there is no evidence to suggest that patient data are not missing at random, we will cautiously conclude that patient data are MAR. Then, multiple imputation techniques will be employed to account for missing data.

Multiple imputation^{21 22} models will be developed to estimate the overall scores for all subjects/visits with missing overall scores. Imputation may be stratified if differences are detected in baseline characteristics between those with or without missing data. The SAS MI and MIANALYZE procedures will be used to conduct multiple imputation.

Determination of Patients/Data for Analysis

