4.4.6 Secondary Objective #6: Quality of life measured by EQ-5D

The secondary objective #6 is to test the hypothesis that the change in health outcome, measured by the EQ-5D, in the aCRT ON group is better than the change in the aCRT OFF group.

Hypothesis

The EQ-5D index will be assessed at baseline and at the 3, 6, 12, 18, and 24 months follow-up visits. Derivation of EQ-5D index will follow instructions provided by the EuroQol Group (www.euroqol.org).

Let α_T and α_C denote the fixed treatment effect on EQ-5D index for aCRT ON and aCRT OFF group, respectively. The null and alternative hypotheses are:

$$H_0 : \alpha_T = \alpha_C$$

$$H_A : \alpha_T \neq \alpha_C$$

Analysis Method

The same general linear mixed models used for KCCQ overall summary score in section 4.4.5 will be used to analyze the EQ-5D score collected over time. Again, in the primary analysis, the model will include the fixed effects of treatment, visit, treatment by visit interaction and baseline EQ-5D score, and two random effects – random site effect and random subject effect. The analysis will be conducted using the SAS MIXED procedure similar to below:

```
proc mixed data=EQ5D method=reml covtest;
id pt;
class pt site rand visit;
model EQ5Dscore = rand visit rand*visit EQ5D_base
/ solution ddfm=satterth covb chisq;
random site pt(rand);
run;
```

where EQ5Dscore is a continuous longitudinal endpoint that includes all post-randomization EQ5D measurements, visit is the categorical version of the visit number. rand*visit is the interaction between treatment and visit, and EQ5D_base is the EQ5D score at baseline. If the interaction between treatment and visit is not significant, it will be eliminated from the model and the main effect of treatment will be used to test the hypotheses; otherwise, if the treatment by visit interaction turns out to be significant, then treatment effect at each visit will be evaluated and the hypotheses will be tested using CONTRAST or LEMESTIMATE statement in the SAS MIXED procedure.

Missing Data

Missing data for EQ-5D score will be handled similarly as those for KCCQ score. Mechanism of missing will be investigated to see if EQ-5D data are missing at random (MAR). Multiple imputation will be used with the SAS MI and MIANALYZE procedures to estimate the EQ-5D scores for subjects that had missing data on this outcome.

Determination of Patients/Data for Analysis

The analysis follows the ITT principle and includes all the randomized subjects.

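### The SAP's mixed models for KCCQ and EQ-5D leave out NYHA class, a randomisation stratum that the protocol requires in both models

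*SAP*

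**What the plan says.** Protocol section 11.5.1 sets the covariates for both questionnaires. For KCCQ: "The baseline KCCQ score as well as the stratification variables included in the primary objective model will be included as covariates in the model". For EQ-5D it names "The baseline EQ-5D index as well as the stratification variables included in the primary objective model" in the same role.

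The primary objective model in Protocol section 11.3.2 is a "Cox proportional hazards regression model with a random center effect (frailty), stratified by baseline NYHA class". SAP section 3 confirms the design: "The randomization will be stratified by two factors: site and NYHA class at enrollment". The stratification variables are therefore center (site) and NYHA class.

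The SAP's KCCQ model is described in words ("the model will include the fixed effects of treatment, visit, treatment by visit interaction and baseline KCCQ score, and two random effects"), written as an equation, and coded as "model KCCQscore = rand visit rand*visit KCCQ_base" with random site and subject effects. EQ-5D follows in words and in code: "model EQ5Dscore = rand visit rand*visit EQ5D_base". Site appears in both models. NYHA appears in neither: it is missing from the prose, from the KCCQ equation, and from both the CLASS and MODEL statements.

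**The concern.** The protocol and the SAP specify different models for two confirmatory secondary tests. Each endpoint then has two documented models and two possible p-values. Hommel works on the ordered p-values of the whole family, so the choice could in principle also affect decisions on other secondary objectives.

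The omission also goes against the usual practice of analysing by the factors used in randomisation. Stratified randomisation largely balances NYHA between arms, so the true sampling variance of the treatment effect already benefits from that balance. A model without NYHA leaves its contribution in the error variance, and the reported standard error is then a little too large.

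**Working it through.** **Text comparison.** Eight secondary objectives less cost-effectiveness, which has no hypothesis test, leaves seven in the Hommel family. Their main models in the SAP are:

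| Objective | SAP section | Site | NYHA |
|---|---|---|---|
| 1 Mortality | 4.4.1 | frailty | stratum |
| 2 HF events | 4.4.2 | frailty | stratum |
| 3 CCS | 4.4.3 | random intercept | covariate |
| 4 AF | 4.4.4 | frailty | stratum |
| 5 KCCQ | 4.4.5 | random effect | **absent** |
| 6 EQ-5D | 4.4.6 | random effect | **absent** |
| 7 Readmission | 4.4.7 | random intercept | covariate |

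Five of seven include NYHA and two do not. CCS is the closest comparison. The protocol asks for analysis "with a logistic regression model, correcting for the stratification variables also included in the primary objective model", nearly the wording it uses for KCCQ and EQ-5D, and there the SAP includes both site and NYHA.

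Elsewhere the SAP announces when it drops a design factor: site in the as-treated analysis (4.3.4), center in the Fine-Gray model for HF events, and both NYHA and center in the recurrent-event model (4.4.2). Sections 4.4.5 and 4.4.6 say nothing, and the SAP version history lists no change to these models. This looks like an oversight.

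**Size.** The plan gives no figure to reproduce. Let R² be the share of variance in patient-level mean scores that NYHA explains once the baseline score is in the model. The documents do not give it; 1%, 3% and 5% are assumed. The reference is a model with NYHA, two-sided 5% level and 80% power, so the standardised effect is 1.960 + 0.842 = 2.802.

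With exact NYHA balance between arms:
- Ratio of confidence interval width, with NYHA to without: √(1 − R²).
- Actual level without NYHA: 2 × [1 − Φ(1.960/√(1 − R²))].
- Power without NYHA: Φ(2.802 − 1.960/√(1 − R²)).

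| Assumed R² | Width ratio | Interval narrower by | Actual level | Power |
|---|---|---|---|---|
| 1% | 0.995 | 0.5% | 4.9% | 79.7% |
| 3% | 0.985 | 1.5% | 4.7% | 79.1% |
| 5% | 0.975 | 2.5% | 4.4% | 78.5% |

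Balance will not be exact, because many center-by-NYHA blocks will be incomplete. Let k be the variance of the NYHA imbalance relative to unrestricted randomisation. Simulation with 3500 patients, 250 centers and assumed NYHA mixes, center sizes and block sizes gave k of 0.19 to 0.37. With v = 1 − R² + kR², the level is 2 × [1 − Φ(1.960/√v)] and the power is Φ((2.802√(1 − R²) − 1.960)/√v). For the three R² values the level is 4.9%, 4.7–4.8% and 4.5–4.6%, and the power is 79.7%, 79.0–79.1% and 78.3–78.4%. The conclusion does not change.

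**The case against.** The strongest case is that this is only a document-alignment point. Site and the baseline score are already in both models, the primary analysis is untouched, and the cost is 0.3 to 1.7 points of power under assumed inputs. Protocol section 11.1 foresees SAP deviations and sends the explanation to the Final Report. SAP section 2 says it was built on protocol Version 1, which is not available here, so the SAP may have matched the text it was written against.

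The small size stands. The version argument may explain the gap but does not close it. The SAP itself names NYHA as a randomisation stratum, and the protocol's change history says that this stratification was in place from the start of the study. SAP version 3.0 is dated 15 November 2021, whereas the current protocol still refers to April 2018 as a future date, so the later SAP could have been aligned. An explanation in the Final Report comes after the analysis and does not settle in advance which model governs.

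Two technical limits also stand. First, the statement of no bias holds for complete data. If missing scores depend on both NYHA and arm, leaving NYHA out of the analysis and the imputation need not be neutral. The SAP covers this only in part, by allowing stratified imputation. Second, R² must be read at the level of patient means. If 5% is instead a single-score figure, then with five complete visits and an assumed within-patient correlation ρ of 0.5 to 0.7, the patient-mean value is 0.05/[(1 + 4ρ)/5], or 8.3% to 6.6%. The level is then 4.1% to 4.3% and the power 77.5% to 78.1%, which is still a modest effect.

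**Conclusion.** The concern holds. NYHA class is required by the protocol and absent from the SAP's KCCQ and EQ-5D models, and nothing shows that the omission is intended. It affects two of seven secondary tests and does not touch the primary objective. With complete data the consequence is slight conservatism and a small loss of precision: at most about 2.5% in interval width and 1.7 points of power for a patient-mean R² up to 5%. That R² is an assumption, and the incomplete-block figures also rest on assumed NYHA mixes, center sizes and block sizes. Any effect through missing data was not quantified. The discrepancy should be resolved because it leaves open which model governs two confirmatory tests, and because resolving it is nearly free.

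**What to change.** In SAP sections 4.4.5 and 4.4.6, add NYHA class at enrollment as a fixed effect to the model description and to the CLASS and MODEL statements, and add the matching term to the equation in 4.4.5. Enrollment NYHA is the variable that SAP section 3 names as the stratum and that the SAP's other models use; Protocol section 11.3.2 calls it baseline NYHA, so one label should be used throughout. If the omission is intended, state it and the reason in the SAP. Either change should be made before the treatment comparison is unblinded.

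The cost is one term in each of two models. NYHA class is already collected, so no new data are needed.

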4 DESCRIPTION OF ANALYSIS

4.1 General

Medtronic employed statisticians will perform the statistical analyses described in this SAP. Interim analyses will be performed by a Medtronic statistician other than the lead statistician for the study. The lead study statistician will be blinded to all interim analyses.

All tests of treatment effects will be conducted in order to preserve an overall two-sided alpha level of 0.05 unless otherwise stated. An Intention-to-Treat analysis will be performed and will serve as the primary analysis for all objectives in this study. The Intention-to-Treat cohort will include all randomized subjects.

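### For KCCQ and EQ-5D, a treatment-by-visit pre-test decides how the hypothesis is tested, and the contrast for a significant interaction is not named, so the p-value sent to Hommel is undefined in that branch

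*SAP*

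**What the plan says.** Protocol 11.5.1 describes one linear mixed model per questionnaire. On treatment it says "The treatment arm allocation will be included as a main effect". On time it says only "Analysis will be corrected for time trends if needed". It mentions no treatment-by-visit term.

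SAP 4.4.5 states one null hypothesis for KCCQ, equality of two parameters that "denote the fixed treatment effect on KCCQ overall summary score for aCRT ON and aCRT OFF group, respectively". Five post-baseline visits supply the data: "The KCCQ questionnaire is collected at baseline and at the 3, 6, 12, 18, and 24 months follow-up visits". The model contains treatment, visit and their interaction, and the test then forks:

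- Interaction not significant: "If the interaction between treatment and visit is not significant, it will be eliminated from the model", and the treatment main effect is tested.
- Interaction significant: "then treatment effect at each visit will be evaluated and the hypotheses will be tested using CONTRAST or LEMESTIMATE statement" (the second statement is presumably LSMESTIMATE).

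SAP 4.4.6 applies the same rule to EQ-5D: "if the treatment by visit interaction turns out to be significant, then treatment effect at each visit will be evaluated".

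Protocol 11.5 and SAP 4.4 promise strict family-wise error control. It is to be achieved by a Hommel procedure over the secondary objectives other than cost-effectiveness, which leaves seven.

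**The concern.** Hommel needs one valid p-value per objective. When the interaction is significant, the SAP does not say which contrast supplies it. The fork also operates when the visit-specific estimates are most spread out, which is when a single visit is most likely to look extreme by chance.

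This is not how the SAP handles the same problem elsewhere. For the primary endpoint, SAP 4.3.2 anticipates a treatment effect that varies over time and ties significance to one named contrast, the 24-month estimate. KCCQ and EQ-5D have no such sentence.

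Two things are at stake: the error rate for two of the seven tested secondary objectives, and the meaning of a positive quality-of-life result, which could be an average over 24 months or something narrower.

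**Working it through.** **Inputs from the documents.** Overall level: "All tests of treatment effects will be conducted in order to preserve an overall two-sided alpha level of 0.05 unless otherwise stated" (SAP 4.1). Five post-baseline visits (SAP 4.4.5). Seven hypotheses in the Hommel family (SAP 4.4). Cumulative alpha for that family of 0.018, 0.031, 0.041 and 0.05 (SAP 4.2 and 4.4).

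**Assumptions, not in the documents.** Between-visit correlation ρ of 0.3 to 0.8; compound symmetry (implied by a random subject intercept); complete data; pre-test level 0.05, with 0.10 as a variant.

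**Step 1: the plan's own figures.** The Pocock-type function 0.05·ln(1 + (e − 1)t) at t = 0.25, 0.5, 0.75 and 1 gives 0.0179, 0.0310, 0.0414 and 0.0500. These match the stated values. The documents give no sample size, power or SD for KCCQ or EQ-5D, so there is nothing else to reproduce.

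**Step 2: structure of the error rate.** Take five visit-wise treatment z-statistics under the null. The interaction test is a chi-square on 4 df of their deviations from their mean. Under compound symmetry, that statistic is independent of the mean. Hence, with a pre-test at 0.05,

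P(reject) = 0.95 × 0.05 + 0.05 × P(reject | interaction significant) = 0.0475 + 0.05 × c.

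The value of c depends on which contrast is used after a significant interaction:

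- Visit average: c = 0.05 by independence, total 0.0475 + 0.0025 = 0.050.
- Any unadjusted visit below 0.05: simulated c is 0.78 (ρ = 0.3), 0.58 (0.5) and 0.384 (0.7). Totals: 0.0475 + 0.039 = 0.0865; 0.0475 + 0.029 = 0.0765; 0.0475 + 0.0192 = 0.0667.

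**Step 3: simulation, 2,000,000 null draws, nominal 0.05, pre-test at 0.05.**

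| Contrast used after a significant interaction | ρ = 0.3 | 0.5 | 0.7 | 0.8 |
|---|---|---|---|---|
| Visit average | 0.050 | 0.050 | 0.050 | 0.050 |
| Month 24 only | 0.057 | 0.055 | 0.053 | 0.052 |
| Bonferroni over five visits | 0.063 | 0.058 | 0.054 | 0.052 |
| Any unadjusted visit | 0.087 | 0.076 | 0.067 | 0.062 |
| Joint 5-df contrast | 0.083 | 0.083 | 0.083 | 0.083 |

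A separate run of 1,000,000 draws over ρ = 0.4 to 0.7 gives 0.050 (visit average), 0.056 to 0.053 (month 24), 0.060 to 0.054 (Bonferroni), 0.082 to 0.066 (any visit) and 0.083 (joint).

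With the pre-test at 0.10, the any-visit reading gives 0.112, 0.094 and 0.078 at ρ = 0.3, 0.5 and 0.7. At the threshold 0.05/7 = 0.0071 (pre-test at 0.05), it gives 0.019, 0.015 and 0.012.

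**Step 4: family-wise error.** Hommel was applied at 0.05 to seven true nulls: five valid independent p-values plus the two questionnaires. The assumptions were ρ = 0.3, 0.5 or 0.7, and a correlation between questionnaires of 0 or 0.6.

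| Reading | Family-wise error |
|---|---|
| Visit average | 0.048 to 0.049 |
| Month 24 only | 0.050 to 0.054 |
| Joint 5-df contrast | 0.059 to 0.061 |
| Any unadjusted visit | 0.056 to 0.072 |

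**The case against.** A reader might infer that the SAP replaces the overall test with five separate tests and lets any visit carry the claim. It does not say so. It says that the effect at each visit is evaluated and that the hypotheses are tested, and the hypothesis stated for each questionnaire is a single equality of treatment effects. A visit-average contrast from the interaction model fits that wording, can be obtained with the statements the SAP names, and holds the error at 0.050. This part of the objection stands: neither inflation nor a single-visit claim follows from the text alone.

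It can also be said that Protocol 11.1 expects the SAP to add detail and requires departures from the protocol to be explained in the Final Report, and that the time component was left partly open. That is fair as far as it goes. But correcting for time trends is not the same as letting an interaction test change which treatment effect is tested, and a later explanation does not restore an error rate.

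What the objection does not remove is the gap. Nothing in either document names the contrast for these two objectives, and apart from the visit average every reading computed exceeds 0.05 per questionnaire.

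**Conclusion.** The point holds in conditional form: once the interaction is significant, the plan defines no single p-value for KCCQ or EQ-5D, so strict family-wise control is not assured. Two stronger statements are not supported: that type I error necessarily exceeds nominal, and that family-wise control necessarily fails. Under the visit-average reading, neither happens.

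The possible effect ranges from none to moderate: up to about 0.08 per questionnaire for ρ of 0.4 to 0.7, and up to about 0.07 for the family in the settings examined. These sizes rest on compound symmetry, complete data, the assumed correlations and an assumed pre-test level of 0.05. A looser pre-test makes the any-visit reading worse. The matter is confined to secondary objectives #5 and #6; the primary test is untouched. It should be corrected, but it does not threaten the trial's main conclusion.

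**What to change.** In SAP 4.4.5 and 4.4.6:

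1. Delete the rule that makes the test depend on the interaction, and keep treatment by visit in the model whatever its p-value.
2. Always test one contrast: the equally weighted average of the treatment differences at months 3, 6, 12, 18 and 24. This matches the protocol's overall treatment effect.
3. State that only this p-value enters Hommel.
4. Report the five visit-specific differences with confidence intervals as descriptive.

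The cost is a sentence and one LSMESTIMATE line per questionnaire, best settled before unblinding. The downside is that a difference confined to one visit could no longer be claimed as significant. Naming the visit average only for the significant-interaction branch would also hold 0.050 under these assumptions, but the unconditional rule is simpler and leaves no pre-test to defend.
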